should likewise have few subjects placed within it. The sensitivity and specificity for assessing each of a mild and a moderate fever temperature will be assessed in a straightforward manner by revealing the labels and determining the fractions of correctly- and incorrectly-labelled datasets. These labels are generated by first matching the NFC UUID associated with an *nfc-temperature-scan* to the previous closest in time *nfc-room-scan* of this same NFC UUID and taking that room's air temperature difference to the temperature scanner's air temperature and converting to simulated core body temperature. Next, this now open-label data will be used to determine the mean and standard deviation across the core temperature scans of each of these four groups. The standard deviation of oral temperatures below the 38C threshold will be used to determine the false positive rate, using an assumed normal distribution or a low-dimensional parametric fit to the actual oral distribution. A parametric fit to the distribution above 38C will be used to determine the sensitivity and specificity for mild, moderate and severe fever thresholds, corresponding to 38-39C, 39-40C and 40C and above, respectively, using the sum of the area under the curve above the appropriate threshold. The linear correlation between oral and imaging temperatures in the below-threshold range will be tested for significance. A subset of the data consisting of equal parts of over-threshold (fevers, by oral temperatures) and under-threshold participants will be tested for significance, and this significance level compared with that of the whole set.

In a second analysis, the controlled face temperature data will be analyzed for effect of confounds with the primary non-contact thermographic system. In this case, the physiologic correction parameters obtained from each individual will be examined for linear correlates or nonlinear relationships with the demographic data. As with the equilibration data, scatter-plots, trends and r-values will be reported, and this data may be collated with future collections of independent datasets.

Quality control and data management

At the conclusion of data collection, the demographic, clinical and thermographic data will be entered into a database. This data will be stored on a password protected PC with access available only to the principal investigator and co-investigators. Raw imaging data will be stored using a unique identifier number for each participant that will be stored in the database. As no identifiers are collected, results will be reported with no individual identifying demographic information.

Timetable

It is anticipated that the study will last between one and two weeks, depending on rate of participant recruitment.

Adverse Events and Data Monitoring Committee (DMC)

Given the minimal risk of the procedures involved in the study the likelihood of adverse events is very low. Overall risk to participants should be no different from that of oral thermometry. Given the very low risk involved no data monitoring committee will be employed for the study. The thermal imaging temperature will not be entered into the participant's clinical report because the

imaging performed does not constitute a complete diagnostic imaging study and should not be considered by the participants as a substitute for the oral thermometry.

E. References

1. Protsiv M et al, "Decreasing human body temperature in the United States since the Industrial Revolution", *eLife* 2020;9:e49555, DOI: 10.7554/eLife.49555, <https://elifesciences.org/articles/49555>
2. Mackowiak PA et al, "A Critical Appraisal of 98.6F, the Upper Limit of the Normal Body Temperature, and Other Legacies of Carl Reinhold August Wunderlich", *Journal of the American Medical Association*, 1992, Vol 268, No 12.
3. Obermeyer Z et al, "Individual differences in normal body temperature: longitudinal big data analysis of patient records", *BMJ* 2017;359:j5468, <https://www.bmj.com/content/359/bmj.j5468>.
4. Sund-Levander M et al, "Normal oral, rectal, tympanic and axillary body temperature in adult men and women: a systematic literature review". *Scandinavian Journal of Caring Sciences*. 16 (2): 122–8. doi:10.1046/j.1471-6712.2002.00069.x. PMID 12000664.
5. Dodd SR et al, "In a systematic review, infrared ear thermometry for fever diagnosis in children finds poor sensitivity". *Journal of Clinical Epidemiology*. 59 (4): 354–7. doi:10.1016/j.jclinepi.2005.10.004. PMID 16549256.

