Given the difficulty of obtaining sufficient febrile participants for assessing these systems, it would be ideal if there were a way of objectively manipulating face temperatures, however until now simple methods such as heated water bottles have had accuracy of at best 5 degrees C, which is too poor for the assessment of these systems in the way they are intended to be used. As a consequence, regulatory agencies and users have not had a way to assess these systems. Based on recent findings, it is possible that nearly all or even all body temperature measurement systems used to-date have relied on bias-to-normal methods due to major confounds. If there were a source of faces with varying temperatures corresponding to mild, moderate and severe fevers as well as healthy temperatures, it would become possible to detect biasing methods. A new method, used in this study, allows the objective manipulation of face temperatures with sufficient accuracy for assessing real-world sensitivity and specificity.

Furthermore, this method requires no special equipment beyond a clinical oral thermometer and control over air temperatures in closed spaces (rooms, large tents having sufficient dimensions for multiple persons to stand, or other controllable spaces, hereafter “rooms”) to within 1C and allows the control of simulated body temperatures with 0.25C accuracy.

The image on the left shows a thermographic core body measurement system that incorporates dual IR calibration sources in the imaging field of view. The image on the right shows general positioning and usage for different height individuals. Once a face is detected within the field of view, the camera collects thermal images which have been corrected for luminance artifact and linearized to the IR calibration sources, and typically reports a core temperature estimate within a second, reporting the result on the display.

The images above show a typical thermal face image as captured by the system, with the results of an automatic thermal face detection system overlain on the subject's face. Below the subject's face and to the sides are the two IR reference targets. It is important to point out that thermal light does not penetrate clothing or common objects such as glass and plastic that is

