transparent to visible light. Also note the subject's left inner canthus is delineated on the image to the left with white specks (the hottest subset of pixels is replaced by white to provide feedback on device operation). The inner canthus is not the eye nor the tear duct, but rather a space on the nasal bridge midway between the eye and the nasion, very close to where eyeglasses with metal wire bridges terminating in a flat soft pad would contact the nasal bridge.

The overall goal of this study is to improve the IR thermometry science by 1) contributing a method for the objective manipulation of face temperatures using environmental air temperature changes and 2) developing a schema to use this method to assess the real-world sensitivity and specificity of non-contact IR core temperature measurement systems in normal, mild, moderate and severe fever groups, corresponding to core temperatures below 38C (100.4F), 38-39C (100.4-102.2F), 39-40C (102.2-104F) and above 40C (104F). This study is relevant for public health risk, because at present, there is no real-world objective test for thermographic febrile temperature screening devices, which significantly hampers the ability of regulatory authorities to identify improperly operating devices. A secondary goal is to determine the impact of potential confounds on non-contact thermographic temperature measurement. This translates to clinical utility, as any confounds could influence the decisions to prioritize the use of such systems. This is also related to public health risk, because the non-contact core body measurement systems the public is now relying on may have unacceptable biases in their determination of core temperature and it is possible they may even induce harm by altering behavior. Additional documentation is provided as a supplement for the review of this study detailing methods for the evaluation of thermographic systems.

B. Research Design and Methods

Study Population

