- NFC identification: the data collected will not be associated with any identifying information, instead being collected on a single printed sheet of paper having a near-field communication (NFC) sticker placed upon it. This NFC sticker will be used to activate the scanner as well as indicate which room a participant is equilibrating within. This is intended to reduce data collection errors as well as to reduce the possibility of personally identifiable information being exposed.
- Temperature measurements: Study participants will undergo non-contact body temperature measurements from several devices as well as an oral thermometry measurement. The non-contact thermal imaging temperature measurements must be

acquired while any eyeglasses are removed and the eyes must remain visible to the thermal imaging system during each measurement. The participant may be seated or standing for the non-contact thermal imaging temperature measurement, and the distance between the measurement system and the participant may be anywhere between 0.45 and 1.5 meters (1.5 to 5 feet). Masks can be worn during thermal imaging without interfering with the measurement.

- Imaging temperature measurements with glasses: Study participants will be asked to try to bring personal sunglasses and/or eyeglasses with them to the study for use in collecting thermal images of their faces while wearing these. Occluding the inner canthus is generally considered a major confound to acquiring an accurate imaging temperature with thermal imaging, and this data will be used to assess the impact of various eyewear on the output.
- Associated data: the ambient air temperatures at the time of each scan, the distance to participant's face, internal system parameters and the thermographs used to measure the imaging-based core body temperature will be stored, associated with the NFC UUID scanned prior to a scan. These thermographs will be encrypted with the public portion of a private/public key pair, the private portion being stored only on a separate password-protected and filesystem-encrypted computer used for analysis of the images. The thermal imaging system's filesystem is also encrypted and protected by a device-specific 160-bit key that is not practically recoverable from the device. System access is restricted by an RSA key and the system's network is protected by an on-device firewall.

Inclusion Criteria

1. Age > 18.
2. Have received a clinical oral thermometry measurement in the past.

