encompassing both areas. The desired target temperatures for the equilibration phase (Rooms D and E above) are 60F and 80F (or 10F lesser than and 10F greater than the building's setpoint), while the desired target temperatures for the blinded temperature phase (Rooms A, B and C) are 68, 75.6 and 83.2F, if the building's target temperature is 68F, otherwise these should be offset with the difference. To obtain these temperatures, three rooms require heating and one room requires cooling. Each of the heated rooms will have a 1500W space heater and the cooled room will have a flexible temporary doorway installed with ductwork to a portable air conditioning unit. A wall-powered thermostat directed to switch by a rectified PID controller is then used to regulate the on/off cycle of each system. The building's airflow via the ductwork into the room may be damped with assistance from building maintenance. An air temperature logging system is set up in each room and in a preliminary study, is used to obtain the time constant and thermal stability of the room with the associated heating and cooling equipment. The key requirement for a suitable room is that the thermal stability must remain within 1C (1.8F) of a single value near the desired setpoint temperature for 10 minutes. Note, during both phases, it is unlikely these exact setpoints will be achieved at all times due to repeated opening and closing of doors, but fortunately this is not essential because ultimately the analysis is dependent on induced surface temperatures and the resulting induced core temperatures will be calculated for each subject based on the actual blinded temperature and the temperature of the room the IR thermometry is done within.

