The rooms will each consist of a portable tent with dimensions of at least 5x5ft base and height of 6ft. The critical requirement of said tent is sufficient thermal isolation from ambient temperatures to allow the maintenance of the required elevated or cooled temperature setpoints to within 1.8F. At present time, the most suitable tent is the THUNDERBAY Ice Cube 3 Man Portable Ice Shelter <https://www.amazon.com/gp/product/B019CU59VI>. This tent is surprisingly large, and has sufficient space to allow four adults to stand with 2 feet between adjacent people or two people with over 3 feet between them. The thermal radiant intensity of the walls of this tent do not match that of the elevated or cooled air temperature, because these walls directly contact and conduct to the ambient air and equilibrate between the ambient and internal temperatures, thus they radiate closer to the ambient temperature. Therefore, additional radiating membranes are used, consisting of sheets of fabric or paper hung from the ceiling or otherwise mounted with at least several inches displacement from the walls and having sufficient but low level of air flow to equilibrate the majority of the membrane to the internal air temperature. A GFCI-protected extension cord and powerstrip will be used to provide power to each tent.

The formula relied upon to obtain the ideal elevated temperatures is as follows, given as a lambda expression, which incorporates a first lambda (Python):

- $core2surf = \lambda core, air: core - (core-air)*0.191$

- $get_needed_room_air = \lambda air, febrile: core2surf(febrile, air) - ((98.6 - core2surf(febrile, air))/0.236)$

This gives us the needed heating temperature to get a desired change in body temperature, e.g. $get_needed_room_air(68, 100.4)$ returns 75.6F, meaning, in order to simulate a 100.4F core

temperature, a person must equilibrate to 75.6F air temperature before returning to receive a scan from the primary scanner located in 68F air temperature. This can be summarized more simply as, for every 1C (1.8F) elevation desired, the heated room must be that multiple of 4.23C (7.62F) above the scanning area's air temperature. Note, the exact coefficient was determined in a pilot study performed in June 2020, and may be refined by this study, which could alter the expected induced core temperatures.

Detailed Procedure - Blinded Temperature Study

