Appendix - Physiologic Model

There is considerable published research on the heat transfer properties of human skin, with the original bioheat transfer equation (Pennes 1948) based on thermal conductivity of tissue, perfusion and blood density. Over the years, modifications were proposed incorporating fluid flow, viscosity and radiative effects (Wulff, Liu) primarily to better model dynamic effects. However, in static equilibrium the theoretical model is approximated sufficiently well by the Fourier heat equation. The model assumes that due to the anatomy of the angular artery, the tissue located a few mm beneath the skin of the inner canthus is at core body temperature. At the surface of the skin, the surface temperature is set by the heat flow through this thin layer of skin and then emitted to the ambient by radiative and convective routes to the air. The conduction through skin can be approximated to be proportional to the delta between core and surface skin temperature divided by a thermal resistance we do not need to know if we know the skin temperature and ambient temperature because the heat flow from core to skin is equal to the heat flow from skin to ambient air.

Radiative dissipation for typical body and ambient temperatures can be linearly approximated to good accuracy as 6 Watts per square meter times the delta in temperature between skin and ambient (C), and radiative dissipation is within an order of magnitude of the conductive plus convective pathway which is also proportional to the delta between skin and ambient temperatures. Because these are proportional to the delta, and if the air conditions are still and not excessively humid, the effect is linearly dependent on the delta and can be measured and used to perform a physiologic correction on the measured surface temperature in order to determine core body temperature to sufficiently good accuracy (0.5C). The primary sources of error in the physiologic correction are the air conditions, which can alter the

convective dissipation to ambient by a factor of two or more, and the thickness and other properties of the skin layer between core and inner canthus skin. Nevertheless, these have been observed by clinical study to be sufficiently consistent from person to person to serve as a modality for obtaining core body temperature. This model is used to perform a physiologic correction taking ambient air temperature to convert an inner canthus skin temperature to a core body temperature.

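### Section D takes the air-derived label as the true simulated temperature and never checks it against measured skin temperature, so a heating shortfall could be misread as device bias-to-normal

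*Combined protocol and SAP*

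**What the plan says.** The first part of the overall goal (A. Introduction) is "contributing a method for the objective manipulation of face temperatures using environmental air temperature changes". The second is to use that method to assess the sensitivity and specificity of non-contact systems. The Introduction adds that the method needs air in the rooms controlled "to within 1C and allows the control of simulated body temperatures with 0.25C accuracy".

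Under Controlled Temperature Rooms, surface temperature is modelled as "core - (core-air)*0.191". To simulate each 1C rise in core temperature, "the heated room must be that multiple of 4.23C (7.62F) above the scanning" area's air temperature. The coefficient comes from a June 2020 pilot and may be refined by this study. The same section says the induced temperature will be computed from the actual temperatures of both the blinded room and the scanning room.

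Section D builds the label by matching each scan to the participant's preceding room, taking the difference between that room's air temperature and the scanner's "air temperature and converting to simulated core body temperature". It then counts correct and incorrect classifications. It expects a good system to place half of the readings above the threshold, and says that a biased one might place only 10% there.

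Section D also plans heating and cooling time constants and a re-estimated offset from the equilibration phase, scan means and SDs by group, and an examination of individual correction parameters. Under Data Collection, the "thermographs used to measure the imaging-based core body temperature will be stored" together with the ambient air temperature at each scan.

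**The concern.** The label is a prediction of what ten minutes in a room should do to a face. Section D uses it as the reference standard. If faces do not fully reach the predicted temperature, or lose part of it on the way to the scanner, an accurate device will read below its label.

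The text itself names routes to a shortfall. The tent walls radiate nearer to ambient (membranes are added to offset this), the Appendix says that air conditions can change convective loss by a factor of two or more, and participants leave the heat before being scanned.

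The planned measurements do not close the gap as written. The equilibration phase scans people seated inside rooms targeted at 60F and 80F, so it covers neither the 83.2F room nor cooling after exit. No rule says how the time constants, the new offset or a refined coefficient enter the blinded-phase labels. The group means are core-temperature outputs of the devices being assessed.

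At stake are both goals: the manipulation method would go untested where it is applied, and a failed manipulation could not be told apart from a device that compresses readings toward normal.

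**Working it through.** **Inputs.** Coefficient 0.191, 4.23C of air per 1C of simulated core, and room targets 68, 75.6 and 83.2F (Controlled Temperature Rooms). SD 0.48F, the stated upper bound for physiologic variability, and SD 1.11F, the observed spread of surface-based data (Population Size). Ten minutes in each room, and secondary scans within one minute of exit (Detailed Procedure - Blinded Temperature Study). The 50% and 10% patterns (Section D).

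**Reproducing the plan's figures.**
- 0.191/(1 − 0.191) = 0.236, and 1/0.236 ≈ 4.24, in line with the stated 4.23.
- The room formula at 68F returns 75.62F for 100.4F and 83.24F for 102.2F, matching the 75.6 and 83.2F targets.
- The simulated shifts are therefore 1.8F (Room B) and 3.6F (Room C). The matching surface shifts are 0.191 × 7.6 = 1.45F and 0.191 × 15.2 = 2.90F.

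**Effect of a shortfall on a perfect device.** Let f be the fraction of shift s achieved, with readings normal around the true value and the label at the threshold. The share above threshold is Φ(−(1 − f)s/SD). With f = 0.80 (an assumption), the deficit is 0.36F in Room B and 0.72F in Room C:

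| SD | Room B | Room C |
|---|---|---|
| 0.48F | Φ(−0.75) = 23% | Φ(−1.50) = 7% |
| 1.11F | Φ(−0.32) = 37% | Φ(−0.65) = 26% |

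**Shortfall that reproduces the 10% pattern.** The deficit needed is 1.2816 × SD.
- SD 0.48F: 0.615F, i.e. 0.615/1.8 = 34% in Room B or 0.615/3.6 = 17% in Room C.
- SD 1.11F: 1.42F, i.e. 79% or 40%.

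**Incomplete warming.** The time constant τ is not given. Assuming a single exponential, f = 1 − exp(−10/τ). For τ from 2 to 10 minutes, f runs from 99% to 63%. The share above the Room B threshold runs from 49% to 8% at SD 0.48F, or from 50% to 28% at SD 1.11F.

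**Cooling before the scan.** Assume the same τ for cooling and a full one-minute delay, so f = (1 − exp(−10/τ)) × exp(−1/τ). With u = exp(−1/τ), f = u − u¹¹, which is largest at u¹⁰ = 1/11 (τ = 10/ln 11 = 4.2 minutes). The maximum is (10/11) × (1/11)^0.1 = 0.715. So at most 71.5% of the shift remains for any τ, and at most about 14% (SD 0.48F) or 32% (SD 1.11F) of Room B scans exceed the threshold. Secondary devices always follow the primary, so they are nearer this limit.

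**The 0.25C figure.** 1C/4.23 = 0.236C, so 0.25C matches one 1C tolerance. If the scan area also varied by 1C (an assumption), control error would be √2 × 0.236 = 0.33C by root-sum-square, or 2 × 0.236 = 0.47C at worst.

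**Could the proposed check see a shortfall?** Assuming an SD of 0.5F for the within-person surface change and 28 participants, SE = 0.5/√28 = 0.094F. A 20% shortfall in Room C is 0.2 × 2.90 = 0.58F, about 6 SE. In Room B it is 0.2 × 1.45 = 0.29F, about 3 SE.

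**The case against.** The strongest reply is that the study does measure closely related quantities. It records serial canthus temperatures in a heated and a cooled room, estimates time constants, re-fits the offset, reports scan means by group and looks at individual correction parameters. The coefficient also has pilot support (32 subjects in June 2020) and a heat-flow model. A reader might infer that the shift is never measured, or that the 0.25C figure is its only support; the documents support neither. What stands is narrower: Section D does not carry any of these results into the blinded-phase labels.

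A reader might also infer that 0.25C is the error of the labels, and that it should be 0.33 to 0.47C. That does not follow. Labels use the actual temperatures of both rooms, so a miss of the setpoint does not enter them if the logs are accurate. The 1C requirement, that a room "must remain within 1C (1.8F) of a single value near the desired setpoint temperature for 10 minutes", is not stated for the scanning area. The plan shows no derivation of 0.25C; that it covers one tolerance is an inference from arithmetic. Nor is the Appendix's 0.5C, an accuracy for converting skin to core temperature, or the 0.36F mean difference in the sample-size argument, a yardstick for it. They are different quantities.

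It is also tempting to say that the plan would declare devices biased. The 10% remark is an illustration of what might be seen, not a decision rule, and a shortfall shared by every device, including the primary, could be noticed. Finally, the 80% is hypothetical, and at SD 1.11F the same shortfall comes nowhere near 10%.

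The plan refers to a supplement on evaluation methods and a Study Schema that are not available here, so the gap is shown only for the protocol text.

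**Conclusion.** The point holds as a gap in the analysis plan. Section D treats a label computed from air temperature as truth and has no planned step that verifies or corrects it from measured skin temperature, so a shortfall in the manipulation could be misread as bias-to-normal.

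The size depends on the SD and on the unknown shortfall. At SD 0.48F the 10% pattern can appear in Room C with only a 17% shortfall; at SD 1.11F it takes 40%. In Room B it takes 34% or 79%, so a 20% shortfall does not reach 10% there under either SD. The delay result rests on one exponential time constant for warming and cooling and on a full minute's delay. The documents do not show that a shortfall will occur; they leave no planned way to rule it out.

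The 0.25C figure is a secondary matter of stating which air temperature it covers.

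**What to change.** 1. Add a pre-specified manipulation check to Section D. Use the primary camera's stored canthus surface temperature, referenced to its IR sources, not its core output. Estimate the within-person change from Room A to Rooms B and C, divided by 0.191 × the logged air difference, in a model with a participant effect. Report the achieved fraction with a 95% CI and its between-person SD.
2. Keep the pre-set labels for the primary sensitivity and specificity. Add a sensitivity analysis with labels scaled by the achieved fraction and, for secondary devices, adjusted for scan delay using logged scan times and the estimated time constant. State in advance whether a refined coefficient changes any label; the Introduction's own objection to thresholds set after seeing the data applies here too.
3. Call a device biased toward normal only relative to the achieved shift. State that the primary camera's surface reading is not an independent reference for the primary system itself.
4. State that 0.25C covers one air temperature and, if the scanning area has a tolerance, give the combined figure.

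The cost is a little more analysis on data already stored, and possibly a less favourable statement of the method's accuracy. The delay adjustment also needs times that the procedures do not clearly provide: room exit, since the described room scan is made inside on arrival, and a time for each secondary reading logged by hand.

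### The plan promises sensitivity above 40C (104F), but no planned room condition produces a severe-fever label

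*Combined protocol and SAP*

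**What the plan says.** The overall goal in section A (Introduction) is partly to develop a schema that uses heated rooms to "assess the real-world sensitivity and specificity of non-contact IR core temperature measurement systems in normal, mild, moderate and severe fever groups". Normal is below 38C (100.4F), mild 38-39C, moderate 39-40C, and severe above 40C (104F).

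Section B, Controlled Temperature Rooms, gives the blinded-phase targets for a 68F building: "Rooms A, B and C) are 68, 75.6 and 83.2F". It also gives the conversion between air and simulated core temperature, with the terms "core - (core-air)*0.191" and "98.6 - core2surf(febrile, air))/0.236".

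Section D (Analyses) says four things that bear on this point:

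- The true label of a scan comes from the difference between the air temperature of the room just left and that of the scanner, converted to a simulated core temperature.
- Direct, label-based sensitivity and specificity are described for mild and moderate fever only. The rooms were chosen so that simulated temperatures fall around those two thresholds.
- After labels are revealed, a mean and SD are to be computed for each of the four groups.
- A parametric fit above 38C, using the area beyond each threshold, is to give "sensitivity and specificity for mild, moderate and severe fever thresholds".

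Section D also says that the severe group "should likewise have few subjects placed within it".

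**The concern.** Sensitivity above 40C needs scans whose true label is above 40C. If the rooms cannot generate such labels, the denominator is zero, and a fitted curve can supply a number only by projecting from milder temperatures.

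The projection assumes that a device behaves above 104F as it does near 102F. That is what an evaluation of this kind should test. Section A argues that testing must reach diagnostically relevant high temperatures because some devices pull readings towards normal. A device that compresses readings only at the top of its range would not be exposed here, yet a severe-fever sensitivity would be published for it.

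**Working it through.** **Inputs.** From Controlled Temperature Rooms: coefficients 0.191 and 0.236, reference core 98.6F, room targets 68, 75.6 and 83.2F, room tolerance 1.8F, and the rule of thumb of 7.62F of heating per 1.8F of simulated core. From section A: severe boundary 104F, claimed accuracy of simulated temperature 0.25C (0.45F), and oral temperature mean 97.9 to 98.6F with SD about 1F. From Population Size: 28 participants required, up to 45 recruited.

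**Step 1: reproduce the plan's figures.** Surface = core − 0.191 × (core − air). Needed room air = surface − (98.6 − surface)/0.236. Scan area at 68F:

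- 100.4F: surface = 100.4 − 0.191 × 32.4 = 94.21; room = 94.21 − 4.388/0.236 = 75.6F.
- 102.2F: surface = 102.2 − 0.191 × 34.2 = 95.67; room = 95.67 − 2.932/0.236 = 83.2F.

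Both match the planned rooms.

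**Step 2: apply the same formula to the severe boundary.** 104F: surface = 104 − 0.191 × 36 = 97.12; room = 97.12 − 1.476/0.236 = 90.9F. That is 22.9F above the scan area. Room C is 83.2 − 68 = 15.2F above it, so it falls 7.7F short.

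**Step 3: the label each condition produces.** Label ≈ 98.6 + (1.8/7.62) × (room air − scan air), with 1.8/7.62 = 0.236.

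| Condition | Air difference | Label |
|---|---|---|
| Room A as planned | 0F | 98.6F |
| Room B as planned | 7.6F | 100.4F |
| Room C as planned | 15.2F | 102.19F |
| Room C 1.8F hot | 17.0F | 102.6F |
| Room C 1.8F hot, scan area 1.8F cool | 18.8F | 103.0F |

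Adding the claimed 0.45F accuracy to the last row gives about 103.5F, still below 104F. Another building setpoint (66 to 72F checked) leaves the Room C label at 102.19F, because the rooms are offset with it. The protocol allows the coefficient to be refined, but 15.2F of heating would reach 104F only at a slope of 5.4/15.2 = 0.355, about 50% above 0.236.

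**Step 4: labels built on each person's own core.** Population Size and Controlled Temperature Rooms can be read this way. At planned temperatures, a severe label needs an own core of at least 104 − 0.236 × 15.2 = 100.41F. Assuming a normal distribution with SD 1F:

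- Mean 97.9F: z = 2.51, 0.6%, about 0.2 of 28 (0.3 of 45).
- Mean 98.6F: z = 1.81, 3.5%, about 1.0 of 28 (1.6 of 45).

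With Room C 1.8F hot throughout, the required own core falls to 99.98F. The range becomes 1.9% to 8.3%, or 0.5 to 2.3 of 28.

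**The case against.** **The plan half-concedes the point.** It expects few severe subjects, confines the label-based analysis to mild and moderate, and says openly that severe figures come from a fit. All of this stands. A reader might infer that expecting few contradicts a count of zero. It does not, because that sentence concerns where device readings are placed in the blinded step. From a 102.2F label, a reading above 104F has probability 0.009% with SD 0.48F (z = 1.8/0.48 = 3.75) and 5.2% with SD 1.11F (z = 1.8/1.11 = 1.62). Such readings would be over-reads, not severe cases. The plan does not say that severe labels are absent or that severe sensitivity is extrapolated.

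**The goal describes a schema.** A reader might infer that the Introduction promises data above 40C. It speaks of developing a way to assess the four groups, so it need not lose the severe class.

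**Specificity.** A reader might infer that severe specificity is equally out of reach. It is not: every planned label is non-severe, so over-reads at 104F can be counted directly (28 × 3 = 84 visits, or 45 × 3 = 135). Only taking specificity from the same fit makes it model-dependent.

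**Tolerances.** The 1.8F requirement concerns stability around a value near the setpoint, so it is not a hard ceiling, and 102.6F should not be read as the highest possible label. But Room C would have to be 7.7F above target, with the scan area at 68F, to reach 104F. That is over four times the tolerance.

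**Conclusion.** The point holds for severe-threshold sensitivity and for the severe group's mean and SD. Under section D's air-difference rule, the expected number of severe labels is zero. The hottest planned label is 102.19F, about 1.8F below the boundary, and it stays near or below 103.5F when the stated tolerances and accuracy are stacked. On the own-core reading, roughly 0.2 to 1.0 of 28 participants would qualify at planned temperatures, which cannot support a sensitivity. A severe sensitivity could only be a model extrapolation.

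This rests on the protocol's own conversion coefficients, on rooms running near target and, for the own-core reading, on normality with SD 1F. Applying the 1.8F tolerance to the scan area as well is an assumption made here. The point does not extend to severe specificity, and it does not show that the room temperatures are wrong for the mild and moderate thresholds.

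**What to change.** In section D:

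- Remove severe-threshold sensitivity and the severe group's mean and SD, and state that sensitivity above 40C was not assessed.
- Limit sensitivity claims to the 38C and 39C thresholds. Note that Room C's planned label (102.19F) sits on the 39C boundary (102.2F), so membership of that class turns on small deviations in air temperature.
- Specificity at 104F, the over-read rate, may stay if it is counted directly from the non-severe labels and not taken from the fit.

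In section A, the four-group schema may stay if the text adds that this study provides no sensitivity data for the severe group.

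The cost is wording and one withdrawn estimate that the design could not support. Room temperatures, procedures and sample size are unaffected.
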